### **Stop Date:**

If only ‘day’ is missing, impute day with last day of the month.

If ‘day’ and ‘month’ are missing, and ‘year’ is not missing, then impute month with ‘12’ and day with ‘31’ (or date of study discontinuation/completion if earlier than 12-31 and year is the same as the year of discontinuation).

If the stop date is completely missing, it will be set to the date of study discontinuation/completion. A stop date will not be applied to ongoing AEs.

The imputed dates will be used to assess whether AEs should be considered as treatment-emergent and if medications should be included in the safety summaries as prior or concomitant, however the original, partial dates will be included in data listings. The duration of AEs will be derived as the AE end date (including imputation date for incomplete AE end date) –AE onset date (imputed date for incomplete AE onset date) +1.

### Treatment-related Adverse Events

Any AE with a relationship to study treatment of “Possibly Related” or “Definitely Related” or missing will be considered a treatment-related AE as determined by the Investigator.

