## 12. SAFETY MEASUREMENTS AND VARIABLES

### 12.1 Adverse Events

The definitions and reporting procedures provided in this protocol comply with the current CFR 21 Part 312. An AE is any untoward medical occurrence or worsening of a pre-existing condition, regardless of its relationship to the investigational medicinal product. An AE can therefore be any unfavorable or unintended sign, including an abnormal laboratory finding, symptom, or disease temporally associated with the use of an investigational medicinal product whether or not considered related to the product. Adverse events that are reported after signing the informed consent but prior to randomization, will be recorded in medical history. Adverse events that are reported after initiation of treatment up until the final study visit phone call on Day 31 will be considered TEAEs. Serious adverse events occurring at any time from informed consent to 28 days after the last dose of treatment with study drug will be reported. Subjects will be monitored for AEs throughout the entire study.

Investigators will ask the subject at each visit if they have experienced any untoward effects since the last study visit. The Investigator or designee will record the following information about AEs on the eCRFs: an AE term or description of the event, severity, event start date, event end date (if known), any action (eg, treatment and follow-up tests), the outcome of the event, and the Investigator's assessment of the relationship to the study treatment.

Even if the Investigator feels there is no relationship to the study drug, all AEs must be recorded in the eCRF.

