### 12.3 Reporting of Serious Adverse Events

On behalf of Spyryx Biosciences, Inc, PRA Drug Safety will be managing SAE processing and reporting to regulatory authorities, as required by local regulations.

In addition to completing all eCRFs related to SAEs, Investigators must report all SAEs to PRA Drug Safety within 24 hours after learning about the event. PRA Drug Safety contact information is provided below:

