#### **PRA Drug Safety Contact Information:**

European Investigative Sites:

Drug Safety Helpline: [contact]  
[contact]  
E-mail: [contact]

North American Investigative Sites:

Drug Safety Helpline: [name] or [name]  
[contact] or [name]  
E-mail: [contact]

To be valid, the initial SAE report must include the following minimal data:

- A reporting source (the Investigator's name and/or site number, and contact information)
- A subject identifier
- The identity of the investigational product
- A SAE term, description, or outcome

The following additional data should be provided as soon as possible, but are not required for the initial report if they are not immediately available:

- Event start date
- Event end date if known
- Severity: mild, moderate, severe, life-threatening, or fatal
- The Investigator's assessment of causality: unrelated, unlikely related, possibly related, probably related, or definitely related
- Any serious criteria that apply to the event (see [Section 12.2](#))

Investigators should submit follow-up reports for SAEs whenever additional pertinent information becomes available, and should provide copies of all pertinent documents such as hospital records, admission and discharge summaries, surgical records, laboratory reports, autopsy reports, and other documents when requested and applicable.

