## 4.0 Introduction

The Statistical Analysis Plan (SAP) Version 1.0 was written and finalized prior to database lock of the first cohort. Version 2.1 of the SAP was revised and finalized prior to the database lock of Cohort 2.

This statistical analysis plan (SAP) describes the methods to be used during the reporting and analyses of data collected under SPYRYX Biosciences Protocol SPX-101-CF-201.

This SAP should be read in conjunction with the study protocol and CRF. For Cohort 1, Version 1.0 of the plan was developed using the protocol dated 14Nov2017 and CRF dated 11MAY2017. For Cohort 2, Version 2.1 of the plan was developed using the protocol dated 14May2018 and CRF dated 17Jul2018. Any further changes to the protocol or CRF may necessitate updates to the SAP.

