## 11.0 Data Review

### 11.1 Data Handling and Transfer

Data will be entered into the clinical database and exported as SAS® datasets. Subsequent datasets will be created using SAS and following standard Clinical Data Interchange Standards Consortium Standard Data Tabulation Model (CDISC SDTM, version 1.3, Implementation Guide version v3.1.3) conventions. Analysis datasets will be created using SAS and following CDISC Analysis Data Model (ADaM, version 2.1, Implementation Guide 1.0) standards.

Medical history and AEs will be coded using the Medical Dictionary for Regulatory Activities (MedDRA), version 20.0 at the time of the analysis to assign a system organ class (SOC) and preferred term (PT) to each event. Prior and concomitant medications will be coded using the World Health Organization Drug Dictionary WHODRUG 2017SEP01 DDE+HD B2 at the time of the analysis.

Additional details can be found in the PRA Data Management Plan and the Data Quality Plan for this study.

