### 12.8.1 Adverse Events

Any condition, event and/or signs and symptoms occurring after signing the informed consent form and before starting study drug treatment should be recorded as medical history in the eCRF. Medical conditions/diseases are considered AEs only if they start or worsen after starting study drug treatment (first application of study drug).

Therefore, an AE includes any condition (including a pre-existing condition) that: 1) was not present prior to study treatment, but appeared or reappeared following initiation of study treatment, or 2) was present prior to study treatment, but worsened during study treatment.

A Treatment Emergent Adverse Event (TEAE) is defined as per Section 8.

Subject incidence of adverse events (AEs) will be summarized by MedDRA system organ class (SOC) and preferred term (PT), severity and relationship to study drug for each treatment group and total. For incidence reporting, subjects will be counted only once within same SOC or PT. All AEs, TEAEs and pertinent subject information will be presented in data listings. Serious adverse events (SAEs), AEs leading to death, and AEs leading to withdrawal from study will be presented in separate listings respectively. An overall summary of AEs will be provided by treatment groups and total.

Missing values for severity will be assigned as 'severe' and missing values for relationship to treatment will be considered as 'related' in the summary.

A summary of AEs by SOC and PT will be tabulated in descending order of frequency by treatment groups and total for the following:

- AEs leading to study discontinuation
- AEs leading to death
- All serious adverse events (SAEs)
- SAEs related to study treatment
- All treatment-emergent AEs (TEAEs)
- Treatment-related TEAEs
- TEAEs by maximum severity. For each system organ class or preferred term, multiple occurrences of events within a subject are counted only once at the highest severity

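### The SAP's definition of a treatment-related adverse event omits 'probably related', a level of the only graded causality scale in the documents; the effect on the tables depends on the unstated eCRF levels

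*SAP*

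**What the plan says.** The SAP, section 8.0, under the definition of treatment-related adverse events, states: "Any AE with a relationship to study treatment of “Possibly Related” or “Definitely Related” or missing will be considered a treatment-related AE".

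SAP section 12.8.1 uses this classification. It plans tables of treatment-related TEAEs and of SAEs related to study treatment. It also plans a summary of adverse events by "severity and relationship to study drug for each treatment group and total". On the classification itself it adds only that "missing values for relationship to treatment will be considered as 'related' in the summary".

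Protocol section 12.3, in the list of data to be supplied for a serious adverse event report, gives the investigator's causality scale as "unrelated, unlikely related, possibly related, probably related, or definitely related".

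Protocol section 12.1 has the relationship recorded on the eCRF for every adverse event, as one of several items ending with "the outcome of the event, and the Investigator's assessment of the relationship to the study treatment". It gives no response levels.

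**The concern.** A rule that splits an ordered scale into related and not related should have a single cut point. This rule names the levels on either side of 'probably related' and omits that level. Programmed literally on the protocol's scale, it would tabulate an event that the investigator judged probably due to the drug as not related, while a weaker rating or a blank one would count as related. That sits badly with the SAP's otherwise cautious handling, in which a missing relationship is set to related and a missing severity to severe.

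What is at stake is the related-event part of the safety report. Safety and tolerability is a stated objective. If the level is in use, the omission can only leave the related counts unchanged or lower them. This describes the omission alone: counting missing ratings as related, in the same sentence of the SAP, can raise the same tables.

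**Working it through.** **Step 1. Apply the SAP rule to the protocol's scale.**

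| Rating (Protocol 12.3) | Counted as related under SAP 8.0? |
|---|---|
| Unrelated | No |
| Unlikely related | No |
| Possibly related | Yes |
| Probably related | **No (not listed)** |
| Definitely related | Yes |
| Missing | Yes |

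The only break in order is at 'probably related'.

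**Step 2. Look for a repair elsewhere.** SAP 12.8.1 repeats only the rule for missing values. SAP 4.1, which lists changes from the protocol, declares no change of causality scale. No section of either document says how 'probably related' is to be classified.

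**Step 3. Ask whether the level reaches the tables.**

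- The five-level scale belongs to the reports sent to the safety group, and these are separate from the eCRF: "In addition to completing all eCRFs related to SAEs, Investigators must report all SAEs to PRA Drug Safety within 24 hours".
- The tables are built from the clinical database. SAP 11.1 says: "Data will be entered into the clinical database and exported as SAS® datasets".
- The eCRF relationship item has no stated levels. SAP 4.0 says that "Version 2.1 of the plan was developed using the protocol dated 14May2018 and CRF dated 17Jul2018", but that CRF is not among the documents reviewed.

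That 'probably related' is a value in the analysis data is therefore an inference, for serious and non-serious events alike. There are two cases:

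- *The eCRF uses the protocol's scale.* Events rated 'probably related' drop out of both related-event tables. The summary by relationship is also affected if it shows a related/not-related split. The SAP text does not say which layout it uses, and the table shells are in a separate document (SAP Appendix 2).
- *The eCRF has no such level.* No event is lost. The SAP still does not state the levels it works from or how they map to the scale in Protocol 12.3.

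**Step 4. Size.** The documents give no counts by causality level, so the number of affected events cannot be computed. What can be given is the weight of one affected subject, meaning one whose only otherwise related events are rated 'probably related':

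- Planned Cohort 2: 45 subjects at 2:1 gives 30 active and 15 placebo. 1/30 = 3.3 percentage points; 1/15 = 6.7 percentage points.
- The safety set counts only dosed subjects (SAP 9.3). In Cohort 1, 46 were randomized and 45 treated, so 46 − 45 = 1 was not dosed. If, as an assumption, Cohort 2 also has one undosed subject, that subject falls in one arm or the other: 1/29 = 3.4 points on active, or 1/14 = 7.1 points on placebo.

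These are 1/n weights and not an estimate of the effect. No figure is given for Cohort 1, which was analyzed under SAP Version 1.

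**The case against.** The strongest counter-argument is that the harm rests on documents not available here. The SAP says that it was written against a specific CRF. It puts its levels in capitals and quotation marks, unlike the protocol's lower-case list, which would fit copying from a CRF codelist that has no 'probably' level. Protocol section 15.2 describes the causality assessment in the progress notes simply as related or not, so the protocol's own wording on causality is not uniform. The five levels for serious events need not carry over to the eCRF. This stands as a limit on consequence: any effect on the tables is conditional. It does not remove the mismatch, since the two documents still disagree and neither gives a mapping.

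A second argument is that the impact is narrow. This is correct. SAP 12.8.1 still provides tables of all TEAEs, all SAEs, discontinuations, deaths and maximum severity, together with full listings. No hypothesis test, success criterion or stated stopping rule uses the related subset. If the summary by relationship shows every level, which the table shells may settle, events rated 'probably related' would be visible there.

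A third is that the per-subject weights apply to any Cohort 2 table and are not evidence about this error. That is also correct, and they are offered only for scale.

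**Conclusion.** The point holds and is minor. Confidence is high that the SAP definition omits a level of the protocol's stated scale and so classifies events out of order on that scale. Whether any event is misclassified depends on the eCRF using that level and on an investigator having chosen it; neither can be established from the documents. The effect may be zero. If it is not, the omission lowers the related counts, with each affected subject weighing about 3.3 to 3.4 points on active or 6.7 to 7.1 points on placebo in Cohort 2. The range assumes the planned allocation and at most one undosed subject.

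**What to change.** Before the Cohort 2 database lock:

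1. Check the relationship codelist in the CRF dated 17 July 2018.
2. If it contains 'probably related', amend SAP 8.0 so that 'Possibly Related', 'Probably Related', 'Definitely Related' or missing counts as treatment-related.
3. If it does not, state the CRF levels in SAP 8.0 and their mapping to related or not related, and reconcile them with the scale in Protocol 12.3.
4. State in SAP 12.8.1, or by reference to the table shells if they already settle it, whether the summary by relationship shows each level or a related/not-related split.
5. Re-run the Cohort 1 related-event tables only if SAP Version 1.0 used the same rule and at least one Cohort 1 event was rated 'probably related'.

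The cost is one codelist check, a phrase in the SAP and one programming condition. The Cohort 1 re-run adds to this only if both of its conditions are met. Settling the definition before lock avoids changing which events count as drug-related once treatment codes may be known.

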### Analysis Visit window

Since the actual visit for a subject may not exactly coincide with the scheduled visit date, the actual visit date is mapped to the study analysis visit as follows:

| Study Analysis Visit | Target Day | Study Day | Interval (days) |
|----------------------|------------|-----------|-----------------|
| Visit 1, Screening   | Varies     | <= -1     | NA              |
| Visit 2, Baseline    | 1          | 1         | NA              |
| Visit 3, Week 1      | 7          | 2 – 11    | 10              |
| Visit 4, Week 2      | 14         | 12 – 21   | 10              |
| Visit 5, Week 4      | 28         | ≥22       | NA              |

For lab assessment and spirometry assessment, if more than one actual visit falls within the same defined window, the visit closest to the target day with non-missing data will be considered for analysis. If two actual visit dates are at the same distance from the target day, the latest visit with non-missing data will be considered for analysis.

All summaries and analyses will utilize analysis visits, where appropriate. Data listings will present actual visit names as recorded in the clinical database. Tabulations will not include rows for unscheduled visits, however, unscheduled visits will be included in listings.

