#### 9.4.4 Withdrawal and Replacement of Subjects

##### 9.4.4.1 Criteria for Subject Withdrawal

In accordance with the Declaration of Helsinki (see Appendix 1, [Section 18.1](#)) and other applicable regulations, a subject has the right to withdraw from the study at any time and for any reason without prejudice to his or her future medical care by the physician or at the institution.

Subjects may also be withdrawn from the study for any of the following reasons:

- A female subject becomes pregnant (See [Section 12.6](#) for details on pregnancy reporting requirements)
- The Investigator may decide that the subject should be withdrawn. If this decision is made because of an intolerable AE or a clinically significant abnormality of a laboratory value, the study medication is to be discontinued and appropriate measures are to be taken. The Sponsor or Sponsor designee is to be notified immediately.
- The subject is unwilling to continue in the study.
- The Investigator stops participating in the study or the Sponsor, for any reason, stops the study.
- The subject or the Investigator decides it in the best interest of the subject to seek another treatment.
- The subject fails to return to the clinic for scheduled visits and does not respond to attempts at communication.

The reason for withdrawal will be recorded in the clinical records and the electronic case report form (eCRF). All subjects who prematurely discontinue the study treatment will undergo an early termination visit (see [Section 10.6](#)). Subjects who are withdrawn from the study will not be replaced. All subjects who are withdrawn or discontinue should be offered other approved medical care.

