#### *9.4.4.2 Evaluations at Withdrawal*

For any subject who is withdrawn before completing all study visits, the Investigator should:

- Perform the procedures included in the early termination visit (see [Section 10.6](#))  
These assessments should be performed as soon as possible after the last administration of the study drug, but in any case, will be performed no later than 14 days after withdrawal or discontinuation of the study treatment.
- Complete all appropriate eCRF pages, providing the date of and explanation for the subject's withdrawal/discontinuation.
- When indicated, arrange for appropriate medical follow-up care for the discontinued subject.

If the subject fails to attend the scheduled early termination visit, the Investigator or designee will make at least 2 attempts to contact the subject by telephone. If the subject does not respond, s/he will be considered lost to follow up.

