#### **10.6 Visit 5: Day 29 ( $\pm$ 2 Days) (Also the Early Termination Visit, If Applicable)**

- CFQ-R (not to be performed for subjects who discontinue early)
- Concomitant medications
- AE assessment
- Vital signs
- Weight and BMI
- Abbreviated physical examination
- Spirometry (the study drug will not be administered)
- 12-lead ECG
- Blood samples collected for hematology and serum chemistry tests, including electrolytes
- Blood sample collected for ADA testing
- Urine samples collected for electrolytes, urinalysis, and urine pregnancy test
- Urine pregnancy test performed
- Collect study nebulizer and unused study drug from previous visit
- Schedule the subject's follow-up telephone call

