### Change from Baseline

Change from baseline (CFB) will be calculated as (value at post-baseline visit – value at baseline). CFB will be calculated for subjects with both a baseline and post-baseline value as applicable. Percent CFB will be calculated as (CFB/baseline)\*100, where applicable. If a baseline or post-baseline value has not been recorded for a parameter, then CFB will not be calculated for that parameter. Subjects with missing CFB values will be excluded from analyses in which CFB is the endpoint unless otherwise noted.

### Study Day 1

The first day of study product administered.

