### 12.6.1 Primary Variable

#### Primary Efficacy Analysis

The primary efficacy endpoint is the change from baseline in ppFEV1 at visit 5 (week 4). The change from baseline in ppFEV1 at each visit (Weeks 1, 2, and 4) will be summarized and compared between each treatment group and placebo. No imputation of missing data will be done for this analysis.

The comparison between each treatment group and placebo will be evaluated by using an analysis of covariance (ANCOVA) model, which will include treatment as the factor, and the stratification factor as a covariate (i.e., baseline lung function categories [ppFEV1 40.0% to 55.0% or 55.1% to 80.0% for Cohort 1] and the concomitant use of hypertonic saline for Cohort 2). Also included in the ANCOVA model for Cohort 2 is baseline ppFEV1. Descriptive statistics will include the number of observations, unadjusted mean, standard deviation, median, first quartile, third quartile, minimum and maximum, and least squares mean. Treatment differences from placebo will be presented and estimated by least squares means from the analysis model along with 95% confidence intervals and associated 2-sided p-values, which are presented for descriptive purposes.

Sponsor: SPYRYX Biosciences

Protocol no: SPX-101-CF-201

---

As described in the power and sample size calculations in Section 6.1, Cohort 1 will be evaluated for success using a two-sided 0.15 significance level. Cohort 2 will be evaluated for success using a one-sided (upper) 0.10 significance level. For Cohort 2, both the one-sided p-value and the lower bound (i.e. one-sided 90% confidence interval) will be presented.

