#### Mixed Model for Repeated Measures

The change from baseline in ppFEV1 at each visit (week 1, 2, and 4) will also be evaluated using a mixed effect model for repeated measure (MMRM).

For Cohort 1, to evaluate treatment differences of ppFEV1 change from baseline across time points (week 1, 2 and 4), a likelihood-based mixed effect model repeated measures (MMRM) analysis will be run on ITT analysis set. The model will include the change from baseline in ppFEV1 as the dependent variable; the treatment, visit and treatment by visit interaction term will be treated as fixed effects, and covariates of baseline lung function category (ppFEV1 40.0% to 55.0% or 55.1% to 80.0% for Cohort 1). Subject will be treated as a random effect.

For Cohort 2, the MMRM analysis will be performed for the change from baseline in ppFEV1 to estimate the treatment difference at Week 4. The model will include all participants in the ITT population, and the dependent variable will be the observed change from baseline in ppFEV1 at each post-randomization visit. Covariates in the model will include the fixed categorical effects of treatment, concomitant use of hypertonic saline, visit and treatment by visit interaction, as well as the continuous fixed covariates of baseline ppFEV1 and baseline ppFEV1 by visit interaction.

Sponsor: SPYRYX Biosciences

Protocol no: SPX-101-CF-201

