#### ANCOVA with Multiple Imputation of ppFEV1

Multiple imputation will be used to explore the effect of missing data on the primary endpoint in Cohort 2 only. All missing ppFEV1 data at baseline and Visit 5 (week 4) will be imputed for all enrolled subjects, utilizing the full conditional specification method (FCS). Missing values will be imputed using treatment, hypertonic saline use, sex, age group, and the ppFEV1 recorded at each time point (including baseline). For this analysis, CFB will be calculated for all subjects following imputation.

An ANCOVA model with treatment as a factor, and concomitant use of hypertonic saline and baseline ppFEV1 as covariates, will be run on the imputed data from PROC MI and results will be combined using PROC MIANALYZE. Further details of the multiple imputation are described in section 12.6.5.

Descriptive statistics of the imputed data combined with observed data will include the number of observations, unadjusted mean, standard deviation, median, first quartile, third quartile, minimum and maximum, and least squares mean. Treatment differences from placebo will be presented and estimated by least squares means from the analysis model along with 95% confidence intervals and associated 2-sided p-value.

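### Should off-drug early-termination spirometry be kept out of the Week 4 analysis window?

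*SAP*

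**What the plan says.** The visit-window table in SAP 8.0 maps actual dates to analysis visits: Days 2-11 are Week 1, Days 12-21 are Week 2, and the last row is "Visit 5, Week 4 | 28 | ≥22". If several spirometry visits fall in one window, the one closest to the target day is used.

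Protocol 9.4.4.1 states that "All subjects who prematurely discontinue the study treatment will undergo an early termination visit". Protocol 9.4.4.2 sets the timing: "as soon as possible after the last administration of the study drug, but in any case, will be performed no later than 14 days", counted from the day on which the subject withdraws or stops treatment. Protocol 10.6 gives the ET visit the Visit 5 procedures, including spirometry but not the CFQ-R.

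For the primary ANCOVA, SAP 12.6.1 says "No imputation of missing data will be done for this analysis", and SAP 8.0 adds: "Subjects with missing CFB values will be excluded from analyses in which CFB is the endpoint unless otherwise noted". In the Cohort 2 MMRM "the dependent variable will be the observed change from baseline in" ppFEV1 at each post-randomization visit. A further analysis fills in missing values: "Multiple imputation will be used to explore the effect of missing data on the primary endpoint in Cohort 2 only". SAP 9.1 makes the ITT set primary for efficacy and groups subjects as randomized, whatever treatment they received.

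**The concern.** Read together, these rules let an appointment date decide whether some early stoppers are analysed. Take a subject whose last dose is on Day 10. Seen on Day 12, the ET value maps to Week 2, there is no Week 4 value, and the subject is left out of the primary ANCOVA. Seen on Day 24, the same subject enters it with a value taken 14 days off drug.

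If the drug effect wears off, off-drug values in the active arm dilute the estimated difference. The MMRM and the multiple imputation use the same windows, so they treat the Day 24 value as observed and cannot show the dilution. Cohort 2 has only about 15 placebo and 30 active subjects, so individual values carry weight. A rule based on treatment status rather than date would look tidier.

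**Working it through.** **Inputs.** From SAP 6.1: 45 subjects at 2:1 (30 active, 15 placebo), SD 7.58, one-sided alpha 0.10, differences 6 to 8, stated power 88% to 97%. From Protocol 7.3.2: 45 treated and 40 completed in Cohort 1, so 5/45 = 11.1% did not complete. Assumed, because the documents do not say: the same rate in Cohort 2 (5 stoppers, 3 active and 2 placebo), last-dose days spread evenly over Days 1-27, and every stopper attending an ET visit at least one day after the last dose.

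**Stated power.** SE = 7.58 × √(1/30 + 1/15) = 2.40. The non-central t gives 88.4% at 6 and 97.8% at 8, which reproduces the plan.

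**Which stop days depend on the visit date.** With last dose on day d, the ET visit falls between d+1 and d+14. The date matters when d+1 ≤ 21 and d+14 ≥ 22, so d = 8 to 20: 13 days. Up to Day 7 the value never reaches Week 4. From Day 21 it always does. A same-day ET visit would add Day 21 to the date-dependent range.

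**Expected number of subjects, out of 5.** The entry column sums, over the date-dependent days, the share of ET dates that fall on Day 22 or later.

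| ET delay (evenly spread) | Date-dependent | Entering Week 4 off drug |
|---|---|---|
| 1-3 days | 5 × 2/27 = 0.4 | 5 × 1/27 = 0.2 |
| 1-7 days | 5 × 6/27 = 1.1 | 5 × 3/27 = 0.6 |
| 1-14 days | 5 × 13/27 = 2.4 | 5 × 6.5/27 = 1.2 |

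The protocol asks for the visit as soon as possible, so the upper rows are the more likely ones.

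**Effect on the result, true difference 6.** Power is by non-central t where all 5 are excluded and by simulation (200,000 trials) elsewhere. It ignores any gain from the baseline covariate.

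| Handling of the 5 stoppers | Expected estimate | Power |
|---|---|---|
| All excluded (27:13, SE 2.56), drop-out uninformative | 6.0 | 85.0% |
| 1 active and 1 placebo counted (28:14), effect fully lost | 6 × 27/28 = 5.8 | about 84.5% |
| All counted (30:15), half the effect kept | (27×6 + 3×3)/30 = 5.7 | 85.7% |
| All counted (30:15), effect fully lost | 6 × 27/30 = 5.4 | 82.3% |

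The last row is a ceiling: every stopper must be counted and every active stopper must have lost the whole effect.

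**Cost of a treatment-status rule.** Setting every ET value to missing at Week 4 removes the 0.2 to 1.2 above. It also removes subjects with a last dose on Days 21-27, who are counted now: 5 × 7/27 = 1.3. In total about 1.5 to 2.5 of 5 stoppers would lose their Week 4 value in the primary ANCOVA.

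**The case for a change.** The strongest case for a change is that the present rule is not a consistent strategy of either kind. A full treatment-policy analysis would seek a Week 4 value from every stopper; an on-treatment analysis would use none taken off drug. The date window takes some and leaves others, and the planned missing-data analyses inherit that choice. Fixing it before lock would take only a few sentences. The description of the mechanism stands, and neither document contains an ET-specific window rule.

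The supporting arguments are weaker. The CFQ-R is not done at ET visits, but that is a collection rule for a questionnaire with a two-week recall. Spirometry is deliberately collected there, so the comparison does not show that ET spirometry should be discarded. The word trough in Protocol 7.3.2 appears in a paragraph of Cohort 1 results. Pre-dose spirometry explains it, and the endpoint definitions do not use it.

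The proposed remedy also has faults of its own. It would drop a subject whose last dose was on Day 27 and who was seen on Day 28, yet keep a completer who finished 28 days of treatment and was seen on Day 31, possibly 3 days off drug. It shifts an ITT analysis towards completers, and the 6.0 it would recover assumes that drop-out is uninformative. An upper limit on the window, such as Day 35, would touch almost nobody and would itself be a date rule.

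**Conclusion.** No change to the plan is needed. The windows are written down in advance and give one answer for each subject: ET spirometry from Day 22 counts as Week 4, and earlier ET spirometry does not. They also stop an ET visit in the first weeks, which shares the Visit 5 column of the schedule, from being counted as a Week 4 result. Using the post-stop values that exist is compatible with SAP 9.1, and subjects without a Week 4 value still contribute to the MMRM and the multiple imputation.

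The effect is small and may be zero: 0.2 to 1.2 subjects entering off drug through the date rule, and about 0.2 off a difference of 6 in the plausible case, less than a tenth of the standard error. Loss of effect biases towards no difference, and no inflation of the false-positive rate is claimed. When half the effect is kept, counting the stoppers gives slightly more power than excluding them (85.7% against 85.0%). Choosing an on-treatment rule would be a trade-off between estimands, not a correction.

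These sizes rest on the assumed Cohort 1 drop-out rate, evenly spread stop days, the 3:2 split and attendance at the ET visit. The Day 8-20 range rests only on the documents' windows and an ET visit 1 to 14 days after the last dose.
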